- a. **Setting:** The study site is the medical intensive care unit (MICU) at Yale-New Haven Hospital (YNHH), York Street Campus and St. Raphael's Campus. Median ICU stay is 3 days. Predominant reasons for admission are sepsis and acute respiratory failure. MICU rooms are private. There is currently a unit-wide sleep promotion protocol which limits care activities from 00:00 to 04:00.
- b. **Design:** Aim 1 and 2, prospective cohort study; Aim 3 pilot randomized controlled trial (RCT). Aim 3 which is not dependent on Aims 1 and 2 will be conducted first.
- c. **Cohort:** We will enroll 100 subjects at risk for ICU delirium. In addition, we will enroll 16 subjects into the pilot randomize control trial.
- d. **Inclusion and exclusion criteria:** This study will focus on adults at an increased risk for ICU delirium. We have selected age ≥ 50 years as an inclusion criteria to study middle-aged to older adults who are at increasing risk for delirium while not overly restricting our sample. We will not restrict patients based on admission severity of illness (APACHE II) because we think this is a critically important confounder and would like to study the effect of the full spectrum of severity of illness on our outcomes. We will exclude patients at significant risk for pre-existing circadian abnormalities (e.g. shift work). We will also exclude patients with co-morbid disease or medication use that makes measurement of urinary aMT6s or actigraphy unreliable. Table 2 lists inclusion and exclusion criteria.

Table 2: Inclusion Criteria	Exclusion Criteria

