Research Design: For Aim 3, we will screen and enroll 16 patients using the same inclusion/exclusion criteria as Aims 1 and 2. We will collect room light levels, circadian measurements, patient characteristics, and ICU care events as before. Patients will be randomized via simple randomization with assignment via random number generator to either usual care (n=5 patients) or to bright light for 4 hours daily (n=5 patients) or to bright light for 8 hours daily (n=5 patients). The bright light intervention will be delivered from 09:00 to 13:00 daily (4 hour group) or 09:00 to 17:00 daily (8 hour group). The bright light will be delivered from study day 2 until study day 5. The bright light will continue if the patient is transferred to the floor. Bright light will be delivered by a free-standing apparatus that delivers 10,000 lux at a temperature 5000K. The device will be placed at the bedside within 36 inches of the patient's head and is expected to provide at least 1,250 lux at the angle of gaze.

To remain in the study, the patient must be in the ICU through D2 (e.g., the first day of potential intervention and the night following). After D2, bright light and other study activities will continue if the patient is transferred out of the ICU to the general medical floor. To maintain as much control of the environment as possible, study patients will be booked only to private rooms on the general medical floor.

If symptoms of eye strain, visual disturbance or headache occur, patients will not continue bright light exposure. These reversible symptoms of direct bright light therapy are unlikely, but they will be tracked as a metric of feasibility under the category of patient tolerance. Feasibility Metrics will include patient acceptance (percent of patients/surrogates who agree to bright light when described to them); patient tolerance (percent of days that patients continue with additional treatments once exposed to bright light); intervention fidelity (percent of time per day that device delivers the planned dose of light); and intervention sustainability (percent of intended intervention days that device is used).

Expected Outcomes: We expect that bright light exposure is feasible, will decrease circadian misalignment, and will increase circadian amplitude.

STATISTICAL CONSIDERATIONS

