Aim 3 Analytical Approach: Feasibility: Based on qualitative analysis, we will judge the intervention as feasible if it achieves at least 70% in each of the feasibility metrics: acceptance, tolerance, fidelity, and sustainability. Effect Size: Circadian abnormalities will be assessed as described under Aim 1. Using multivariable logistic regression, we will test for associations between bright light exposure and decreases in circadian misalignment and increases in circadian amplitude. The estimated association will inform the effect size in the design of future interventional studies.

SUBJECT POPULATION

Patients admitted to the Medical ICU and who meet inclusion / exclusion criteria will be recruited into this study. Decisionally impaired persons, females of childbearing potential and pregnant women who are admitted to the MICU and who meet inclusion / exclusion criteria might be recruited into this study; however, they will not be specifically recruited and subjects will be ≥ 50 years old and severe chronic brain injury is an exclusion criteria.

Table 2 (repeated)

Inclusion Criteria	Exclusion Criteria

- Hospital admission less than 30 hours as of noon on day of enrollment- Expected to stay in the MICU ≥ 24 hours after enrollment- Expected to produce ≥ 250 mL urine / day- Age ≥ 50 years- Able to understand English.	
At significant risk for pre-existing circadian abnormalities:
 
- Severe chronic brain injury (Injury greater than 30 days ago resulting in the inability to live independently) OR Acute brain injury of any severity (Injury less than 30 days ago including acute intracranial bleed, traumatic brain injury, central nervous system infection, tumor, hepatic encephalopathy)- Documented circadian disorder (<1% population) or blind/disease of the optic nerve- Current history of substance abuse including alcohol (use in last 30 days)- Transferred from an outside hospital- Homeless 
Unable to participate in study activities:
 
- History of bipolar disease (Bright light therapy possibly unsafe in this population).- Paralyzed (due to injury, disease or medications)

RECRUITMENT PROCEDURES

Patients will be screened daily from an automated list generated from the YNHH EMR. Patients who opt out of research participation via MyChart (patient information portal) will be excluded from this list.

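### Aim 3 enrolls 16 patients, but its three arms of 5 total 15, and simple randomization does not deliver 5 per arm

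*Combined protocol and SAP*

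**What the plan says.** Project Overview, item c (Cohort), states that "we will enroll 16 subjects into the pilot randomize control trial". The Aim 3 Research Design repeats the total: "we will screen and enroll 16 patients using the same inclusion/exclusion criteria as Aims 1 and 2". Two sentences later comes the allocation: "Patients will be randomized via simple randomization with assignment via random number generator to either usual care (n=5 patients"), followed by a 4-hour light arm and an 8-hour light arm, each also with 5 patients. No block, cap or allocation list is described, and no allocation ratio is given.

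The same section sets the exposure period ("The bright light will be delivered from study day 2 until study day 5") and a retention condition ("To remain in the study, the patient must be in the ICU through D2"). It gives no replacement rule, over-enrolment allowance or dropout rate.

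The Aim 3 Analytical Approach sets the feasibility rule: "we will judge the intervention as feasible if it achieves at least 70% in each of the feasibility metrics". For the effect size it says: "Using multivariable logistic regression, we will test for associations between bright light exposure and decreases in circadian misalignment".

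**The concern.** There are two faults in one short paragraph.

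First, the enrollment total and the arm sizes disagree by one patient. Aim 3 has no power or sample-size formula, so the gap cannot be rounding; arm counts have to add up to the total. As written, staff cannot tell whether enrollment ends at 15 or 16, or where the extra patient goes.

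Second, the named method does not produce the stated arms. Independent random draws give arm sizes that vary, and with about 15 patients they vary a lot relative to 5. The plan does not say what happens once an arm reaches 5. An improvised cap would be an undocumented departure from simple randomization.

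The arm split matters for both purposes of the pilot. The Aim 3 Rationale and Analytical Approach say the pilot will inform the effect size of a later trial, and that contrast depends on having enough usual-care patients. Tolerance, defined as "patient tolerance (percent of days that patients continue with additional treatments once exposed to bright light"), fidelity and sustainability accrue only in light-treated patients, and each is judged against 70%.

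**Working it through.** **Inputs.** Total 16 (Project Overview; Aim 3 Research Design). Arms 5, 5 and 5 (Aim 3 Research Design). Light on study days 2 to 5, at most 4 days per patient. Assumed: probability 1/3 per arm, because the equal arm sizes imply it but no ratio is stated; independent draws; and the printed 5s do not act as caps.

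**Total.** 5 + 5 + 5 = 15, against 16. Three equal arms from 16 would be 16/3 = 5.33, not a whole number.

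**Chance of the planned split.** P(a, b, c) = n! / (a! b! c!) / 3ⁿ.

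- n = 15, 5/5/5: 756,756 / 14,348,907 = 0.0527.
- n = 16, 5/5/5: impossible.
- n = 16, 6/5/5 in any order: 3 × 2,018,016 / 43,046,721 = 0.141.

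**Group sizes.** The usual-care count K is Binomial(n, 1/3), and the light total is n − K.

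| Event | n = 15 | n = 16 |
|---|---|---|
| Usual care 3 or fewer | 20.9% | 16.6% |
| Usual care 2 or fewer | 7.9% | 5.9% |
| Smallest of the three arms 3 or fewer | 58.9% | 47.8% |
| Light patients 8 or fewer | 20.3% | 12.7% |

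**Precision (illustration only).** Take an unadjusted difference between usual care and the pooled light arms with equal variances. This is not the planned logistic model, for which the plan does not define how light exposure is coded. Relative to a fixed 5 versus n − 5,

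SE ratio = √[(1/k + 1/(n − k)) / (1/5 + 1/(n − 5))].

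The standard deviation cancels. For n = 16:

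- k = 6: √[(1/6 + 1/10) / (1/5 + 1/11)] = 0.957.
- k = 3: 1.188.
- k = 2: 1.402.

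Averaged over the binomial, leaving out draws with an empty group, the SE ratio is 1.036 and the variance ratio 1.097 with 16 patients; with 15 they are 1.058 and 1.144. With 16, the SE is smaller than at 5 versus 11 in 45% of draws (K from 6 to 10).

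**Planned light days.** 10 light patients × 4 = 40; 11 × 4 = 44; 8 × 4 = 32. So 32 days or fewer has a 12.7% chance with 16 patients and 20.3% with 15.

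**Predictability of a fixed list.** The expected length of the final run of same-arm assignments in a random permutation is 1.36 for 5/5/5 and 1.38 for 6/5/5.

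**The case against.** The strongest reply is that 16 counts patients enrolled and the 5s count patients assigned. Enrollment is on day 1, light starts on day 2, a patient must be in the ICU through day 2 to remain, and the time of randomization is not stated. Sixteen enrolled with 15 in arms is therefore possible. That is fair as a possibility, but the plan never links the retention rule to the count, and it says nothing about how a replacement's arm would be assigned. This reading is one way to reconcile the numbers once it is written down.

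A second reply is that the sentence could mean random assignment to fixed counts, in which case the probabilities above do not apply. The usual meaning of simple randomization is against this, but the wording is ambiguous. If the 5s are caps, the text should say so.

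A third reply concerns size. The SE is equal to or smaller than at 5 versus 11 in about 66% of draws with 16 patients. The two tails also offset: few usual-care patients means more light days, and 8 versus 8 is the best split for the contrast (SE 7% lower). The feasibility percentages carry no precision target, and acceptance does not depend on the split. All of this stands. It limits the harm to an avoidable tail but does not remove the mismatch.

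**Conclusion.** The concern holds. The total of 16 and the three arms of 5 are not reconciled anywhere in the plan, and this needs no assumption beyond addition. Under the standard meaning of simple randomization with equal probabilities, the stated arms are also unlikely at 15 (5.3%) and cannot occur at 16.

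The consequence is moderate. Validity is not affected and the average precision loss is a few percent, but there is a 17% chance (16 patients) or 21% chance (15) of a usual-care arm of 3 or fewer. At 3 versus 13 the illustrative SE is 19% larger than at 5 versus 11, and at 2 versus 14 it is 40% larger. The arm-size probabilities rest on the 1/3 assumption and on the 5s not being caps; the SE figures rest further on the unadjusted pooled contrast. If 5 was meant as an approximate expectation, the plan should say so, and with 16 patients that expectation is 5.33. The change is worth making because it is cheap.

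**What to change.** 1. Make the total in the Project Overview and the Aim 3 Research Design agree with the arms. There are three options: 15 as 5/5/5; 16 with the arm of the extra slot named; or 16 with a sentence saying that the sixteenth replaces a patient who does not meet the day 2 retention rule, and how the replacement's arm is assigned.
2. In the Aim 3 Research Design, replace the wording on simple randomization with: *assignment from one concealed list, generated before enrollment as a random permutation of the planned allocation*. If simple randomization is kept, replace each fixed 5 with *about 5 expected*.

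Which arm takes any extra slot is the sponsor's choice. Usual care slightly helps the contrast (SE 4% lower at 6 versus 10 than at 5 versus 11); a light arm adds planned light days (44 rather than 40).

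The cost is one number or one explanatory sentence in two places, one sentence on randomization, and a pre-generated list. The list has two limits. The device is visible at the bedside, so staff who know the arm totals could deduce about 1.4 final allocations on average, against none under simple randomization. The list also fixes the numbers randomized, not the numbers analysable after the day 2 rule.

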 - ii. The protocol will be described to the patient; this description will include an overview of student events they already completed, cover in detail the study intervention and any remaining/future study procedures/events, and cover the risks associated with participation.
 - iii. We will assure study subjects that participation is voluntary and that the decision to continue their participation will have no impact on their current or future care.
 - iv. A copy of the consent document will be provided to the patient.
- f. **Timeline of Study Activities (Fig 2):** Patients will be enrolled within 30 hours of hospital admission and before 12:00 on the day of enrollment which is designated “Study Day 1 (D1).” Actigraphy, delirium monitoring, and light measurement (part of feasibility) will start no later than 12:00 on D1. Actigraphy and light measurement will continue until D5 or MICU discharge whichever is longer. If the patient is discharged from the hospital prior to day 5, all study activities stop upon hospital discharge. Study activities will continue if/when the patient is transferred to the general medical floor if the patient completes at least D2 (13:00) in the MICU. Delirium monitoring will occur until D30 or hospital discharge.

[figure not shown]

Figure 2: Study activities timeline.

APPROACH TO AIMS

Aim 1: Determine the association between ICU day-night light patterns and circadian abnormalities (i.e., circadian misalignment and decreased circadian amplitude).

Rationale: Aim 1 will test our hypothesis that non-circadian ICU light patterns are associated with increased circadian abnormalities as measured by urinary aMT6s. Our approach is to measure light levels (10-second intervals) and aMT6s (1-hour intervals, gold standard) for 72 hours following study enrollment; we will also collect exploratory measures of circadian rhythm, namely, actigraphy and heart rate. We will collect descriptive patient data to allow model adjustment during analysis. We define non-circadian ICU light patterns as abnormally low daytime light levels and abnormally high overnight light levels. We define circadian abnormalities as circadian misalignment and decreased circadian amplitude. The absence of circadian rhythm is an extreme decrease in amplitude (i.e., 100%). *This work will establish if non-circadian ICU light patterns are associated with the development of circadian abnormalities.*

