Research Design: We will enroll 100 subjects at increased risk for ICU delirium; subjects will be screened and consented as above. We will collect the following measures:

- a. **Room light levels** will be monitored from enrollment until Study D5 or until MICU discharge. We will set the light meter (HD450, Extech Instruments, New Hampshire) to read levels in lux at 10-second intervals. Meters will be placed in a standard location on the wall above the head of the bed as close as possible to eye level. Additional light measures will be taken adjacent to the patient's face (by holding the light meter next to their face for several seconds); these measures will be taken several times per day to assess light levels at or close to the eye.
- b. **Urinary aMT6s (1-hour intervals)** is the primary circadian measure for this aim. Melatonin is normally released just before habitual sleep time, and peak levels occur during sleep midpoint; urinary aMT6s peaks 2 hours after sleep midpoint.³⁸ For the proposed study, urinary aMT6s will be collected for 72 hours or until MICU discharge whichever occurs first. Urinary aMT6s will not be collected after MICU discharge. A 10mL aliquot of pooled urine sample collected every 1 hour will be used for analysis; total volume of urine will be recorded to allow for calculation of total aMT6s excreted. Total aMT6s excreted can be measured and is valid in patients with acute kidney injury, patients receiving diuretics,³⁹ and patients with decompensated cirrhosis.⁴⁰ We have the support of MICU nurse champions and the agreement of nursing leadership for the bedside nurse to collect these samples. Samples are stable at room temperature for 24 hours, will be transported to the lab daily, and stored at -80°C in the Translational Research Core. Samples will be batched and subsequently analyzed using a highly sensitive, competitive ELISA kit (IBL Laboratories, Germany).
- c. **Secondary measures** of actigraphy, surface body temperature, and continuous heart rate monitoring will be used in an exploratory manner. We plan to examine correlation with urinary aMT6s for use in future studies.

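### Aim 3 names neither a baseline cycle nor an outcome window for aMT6s, although its 72-hour urine window holds one night before any light and at most two of the four nights that follow a light session

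*Combined protocol and SAP*

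**What the plan says.** **Light.** Aim 3, Research Design: "The bright light will be delivered from study day 2 until study day 5". Sessions run 09:00-13:00 in the 4-hour group and 09:00-17:00 in the 8-hour group, and they continue if the patient moves to the floor.

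**Urine.** Aim 3 has no aMT6s schedule of its own. Its Research Design says "We will collect room light levels, circadian measurements, patient characteristics, and ICU care events as before", which points back to Aim 1. There the Rationale gives "aMT6s (1-hour intervals, gold standard) for 72 hours following study enrollment", and the Urinary aMT6s item says "urinary aMT6s will be collected for 72 hours or until MICU discharge whichever occurs first" and "Urinary aMT6s will not be collected after MICU discharge".

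**Clock.** Project Overview, Timeline of Study Activities: "Patients will be enrolled within 30 hours of hospital admission and before 12:00 on the day of enrollment". That day is D1.

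**Analysis.** Statistical Considerations, Aim 3 Analytical Approach: "Circadian abnormalities will be assessed as described under Aim 1". Logistic regression then relates bright light to decreases in misalignment and increases in amplitude, and the result is meant to inform the design of later trials. No baseline night is named, and nothing says which nights form the outcome.

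**Other measures.** Under the Timeline section, actigraphy and light measurement run to D5 or MICU discharge, whichever is longer. Aim 1 treats actigraphy as exploratory and bases the assessment against light patterns on aMT6s alone.

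**The concern.** The Aim 1 urine schedule was written for an observational cohort, where every sampled hour has the same status. In Aim 3 the hours differ: some come before any light, some follow one session and some follow two. Two consequences follow.

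First, randomised arms have an expected difference of zero on the night before light starts. If that night enters the outcome together with the later nights, any real effect is attenuated. The night would be more useful as a pre-treatment covariate, especially with the listed groups of 5 patients each.

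Second, the nights that would show the result of the D4 and D5 sessions are not sampled for aMT6s. A reader of the pilot could take its effect size as that of the D2-D5 course, when it can reflect at most two light days.

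The effect size is one of the two stated purposes of Aim 3, so what it measures should be fixed in advance.

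**Working it through.** Aim 3 gives no power or detectable-effect figure, so there is none to reproduce. The check overlays the clock times.

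**Inputs.** Urine: 72 h from enrollment before 12:00 on D1 (Timeline; Aim 1). Light: from 09:00 on D2, D3, D4 and D5 (Aim 3, Research Design). Night: 22:00-06:00, the overnight period in the Aim 1 Analytical Approach. Assumption: urine starts between 08:00 and 12:00 on D1.

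**1. Window.** Noon D1 + 72 h = noon D4. 08:00 D1 + 72 h = 08:00 D4.

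**2. Hours before light.** Noon D1 to 09:00 D2 = 21 h, and 21/72 = 29%. 08:00 D1 to 09:00 D2 = 25 h, and 25/72 = 35%.

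**3. Nights.**

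| Night | Sessions before it | aMT6s window |
|---|---|---|
| D1/D2 | 0 | inside |
| D2/D3 | 1 | inside |
| D3/D4 | 2 | inside, if still in the MICU |
| D4/D5 | 3 | outside |
| D5/D6 | 4 | outside |

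The table is the same for both start times.

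**4. Light hours inside the window.** Noon start: 4 + 4 + 3 = 11 of 16 h (4-hour group) and 8 + 8 + 3 = 19 of 32 h (8-hour group). 08:00 start: 8 of 16 h and 16 of 32 h. At most 3 h of the D4 session is covered, and none of the D5 session.

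**5. Dilution if the three nights are averaged equally.** This is an assumption; the plan does not say it. Let e1 and e2 be the arm differences after one and two sessions. The average is (0 + e1 + e2)/3 = (2/3) × (e1 + e2)/2, that is, two thirds of the mean over the two post-light nights. Against the effect of the full course, the result depends on an assumed time course:
- Immediate and constant effect: (0 + 1 + 1)/3 = 0.67.
- Build-up of 25% of the full-course effect per session: (0 + 0.25 + 0.50)/3 = 0.25. Without the pre-light night it is (0.25 + 0.50)/2 = 0.375, so most of this shortfall comes from the unsampled later nights.

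A single 24-hour cosinor fitted to 72 hourly values agrees. With an immediate effect, a 100 ng amplitude shift is returned as 66.7 ng and a 60-minute phase shift as 40.1 minutes. With the gradual build-up, the same full-course effects are returned as 25.0 ng and 15.0 minutes.

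**6. Early discharge.** A patient who supplies only D1/D2 and D2/D3 gives (0 + e1)/2, half of the one-session effect, under the same averaging.

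**7. Passages that do not agree.** The Timeline section lets study activities continue on the floor once the patient has completed D2 to 13:00 in the MICU. Aim 3, Research Design requires the ICU through the night after D2. Under the first rule a patient could supply no post-light night for aMT6s; under the second, at least one. Aim 3, Research Design also says other study activities continue after transfer, whereas the Aim 1 urine item stops aMT6s at MICU discharge.

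**The case against.** **Pooling is not stated.** No section says that the three nights are averaged. The Aim 1 analysis mentions longitudinal cosinor techniques, evaluation of trend, and generalized estimating equations for repeated outcomes. The Aim 3 section speaks of decreases and increases, which may imply a starting value. All of this is compatible with per-cycle outcomes and D1/D2 as the reference. The objection stands: the defect is an unspecified baseline and outcome window. It does not remove the problem, because whole-window derivation is equally compatible with the text. The estimating equations are also written for Aim 1 with light dose ratio as the exposure, while Aim 3 names logistic regression without a per-night contrast.

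**The noise is larger than the dilution.** With the SD of 95 minutes from the Aim 1 power calculation and 5 against 5 patients, the 95% half-width is 2.306 × 95 × √(1/5 + 1/5) = 139 minutes. For 10 against 5 it is 2.160 × 95 × √(1/10 + 1/5) = 112 minutes. Losing 20 minutes of an assumed 60-minute effect lies well inside that. This stands as a reason for lower priority. It also supports using the pre-light cycle as a covariate.

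**Randomisation puts the pre-light night in every arm.** True, but that makes the expected difference on that night zero, which is the source of the attenuation.

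**Practical limits.** Urine comes only from catheters already in place and is collected by MICU nurses, and "Median ICU stay is 3 days". This explains why the window is short. It does not settle how the collected cycles should be used.

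**Conclusion.** The timing mismatch holds for both start times checked: one pre-light night, at most two post-light nights, and no aMT6s after the D4 and D5 sessions. Whatever the analysis, the effect size cannot represent the D2-D5 course. Dilution by the pre-light night is conditional. It occurs if the measures are derived over all 72 hours, and the factor of about two thirds assumes equal averaging and, when set against the full effect, an immediate and constant response.

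A reader might infer more than the documents support:
- *That the plan pools the nights.* It is silent.
- *That a later trial would be 2.25 times too large, from (60/40)².* This adds a difference-in-means model to the assumed averaging and time course. The stated model is logistic, so its error would not take that form.
- *That the median stay shows how many treated nights patients lose.* The median is unit-wide. Eligibility requires an expected MICU stay of at least 24 hours after enrollment, and the Aim 3 section requires the ICU through the night after D2. Some patients will probably lose D3/D4, but the documents do not allow a count.
- *That nothing is measured after the MICU.* Actigraphy can continue on the floor, though only as an exploratory measure.

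The feasibility metrics do not depend on aMT6s. The plan should be corrected, but the pilot does not fail without it.

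**What to change.** In the Aim 3 Analytical Approach:

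1. Derive misalignment and amplitude per cycle, cut at 09:00 in all arms. A cut at the end of the first session would differ between the light groups and be undefined in usual care.
2. Use the cycle before 09:00 D2 (about 21-25 h) as each patient's baseline covariate.
3. Estimate the arm contrast only from 09:00 D2 to 09:00 D3, and from 09:00 D3 to the end of collection (about 09:00 D4).
4. Report the result as the effect after at most two light days.

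Also reconcile the two rules on how long a patient must remain in the MICU around D2, and the two statements on whether aMT6s continues after transfer.

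**Cost.** A few sentences, using samples already planned; the light intervention is untouched and urine collection need not be extended. Each patient contributes one fewer outcome cycle, the baseline may fall slightly short of 24 hours, and the covariate uses one degree of freedom in a very small trial. Since Aim 3 is conducted first, the text should be settled before its aMT6s data are analysed.

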
1. Hospital admission less than 30 hours as of noon on day of enrollment2. Expected to stay in the MICU ≥ 24 hours after enrollment3. Expected to produce ≥ 250 mL urine / day4. Age ≥ 50 years5. Able to understand English.	
At significant risk for pre-existing circadian abnormalities:
 
– Severe chronic brain injury (Injury greater than 30 days ago resulting in the inability to live independently) OR Acute brain injury of any severity (Injury less than 30 days ago including acute intracranial bleed, traumatic brain injury, central nervous system infection, tumor, hepatic encephalopathy)– Documented circadian disorder (<1% population) or blind/disease of the optic nerve– Current history of substance abuse including alcohol (use in last 30 days)– Transferred from an outside hospital– Homeless 
Unable to participate in study activities:
 
– History of bipolar disease (Bright light therapy possibly unsafe in this population).– Paralyzed (due to injury, disease or medications)

- e. **Recruitment:** Patient recruitment will follow Yale University consent procedures, and we will obtain HIC approval before starting study activities. MICU admissions will be screened daily via the EMR. Eligible patients will be approached within 30 hours of hospital admission. Before consent, the patient will be assessed for delirium via the Confusion Assessment Method for the ICU (CAM-ICU). If not delirious and able to communicate, the patient can provide consent; otherwise, a legally authorized

representative (LAR) as delineated by Connecticut State Law can provide consent.

- a. In cases which the LAR provides consent, assent from the patient will be attempted daily and obtained whenever possible via simple verbal explanation of the purpose, activities, risks and benefits of the study.
- b. In the event a patient originally enrolled via LAR were to regain their capacity to consent themselves, trained study staff will follow the below protocol for re-consent.
 - i. Study staff will introduce identify themselves as a member of the research team and clarify that they are not part of the primary ICU team.

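### Aim 3 removes randomised patients who leave the ICU early, under two conflicting cut-offs and with no stated analysis set or feasibility denominator

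*Combined protocol and SAP*

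**What the plan says.** Four places in the combined protocol and SAP bear on this.

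- **Aim 3 Research Design** states the retention rule: "To remain in the study, the patient must be in the ICU through D2". A parenthesis there extends this over the first possible day of light and the night after it. The text continues: "After D2, bright light and other study activities will continue if the patient is transferred out of the ICU to the general medical floor".
- **Project Overview, Timeline of Study Activities**, written for the whole project, says that activities go on when a patient is "transferred to the general medical floor if the patient completes at least D2 (13:00) in the MICU".
- **Table 2** asks only for "Expected to stay in the MICU ≥ 24 hours after enrollment". The timeline puts enrollment before noon on D1.
- **Aim 3 feasibility metrics** include "intervention sustainability (percent of intended intervention days that device is used". Aim 3 Analytical Approach calls the intervention feasible only if acceptance, tolerance, fidelity and sustainability each reach at least 70%.

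Aim 3 Analytical Approach names no analysis population, denominator rule, replacement rule or missing-data rule. The time of randomisation is not given.

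**The concern.** A patient transferred to the floor at 18:00 on D2 stays in the study under the timeline and leaves it under Aim 3 Research Design. Staff cannot follow both. Under either rule the decision comes after assignment, and for some patients after light has been delivered.

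Two results are exposed. The first is the feasibility verdict. Every metric must pass, so one metric can decide it, and sustainability depends on whose intended days are counted. The second is the effect size, which the Aim 3 Rationale carries forward to a larger trial. With five patients per arm, one removal is 20% of an arm. ICU departure by D2, whether through recovery or death, is plausibly related to outcome. A set filtered on it no longer has the full protection of randomisation.

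**Working it through.** Aim 3 has no sample-size or power calculation to reproduce. The check compares the rules in time and then works an illustration.

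**1. The cut-offs on one clock (hours after noon on D1)**
- Entry criterion: 24 h, about noon on D2.
- Timeline rule: 13:00 on D2 = 25 h.
- Aim 3 rule: D2 and the following night, read here as ending between 06:00 and 09:00 on D3 = 42 to 45 h.

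The two retention rules differ by 42 − 25 = 17 h to 45 − 25 = 20 h. The entry criterion falls 1 h short of the timeline rule and 18 to 21 h short of the Aim 3 rule.

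**2. Order of events**
Light runs 09:00-13:00 or 09:00-17:00 from D2. Anyone treated on D2 must have been assigned before 09:00. By 13:00 the 4-hour arm has had its whole D2 session and the 8-hour arm 4 of 8 hours.

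**3. How many patients the rules might remove (assumption)**
The setting description gives a median ICU stay of 3 days. Assume that the remaining stay is exponential with median m hours, given that the patient stays the first 24 h. The share gone by hour h is then 1 − 2^(−(h − 24)/m).
- m = 72, timeline rule: 1 − 2^(−1/72) = 1%.
- m = 72, Aim 3 rule: 1 − 2^(−18/72) = 16% to 1 − 2^(−21/72) = 18%.
- m from 48 to 96, Aim 3 rule: 12% to 26%, that is 1.2 to 2.6 of 10 light patients.

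**4. Sustainability (assumption)**
The planned arms give 5 + 5 = 10 light patients. (The text says 16 are enrolled, but the three arms sum to 15; this is not explained.) D2 to D5 is 4 intended days, so 40 in all. Let retained patients use the device on 80% of intended days, and let d patients be removed. Days used by retained patients = 0.8 × 4 × (10 − d).

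| Handling of removed patients | d = 1 | d = 2 | d = 3 |
|---|---|---|---|
| Their days dropped from the denominator | 28.8/36 = 80% | 25.6/32 = 80% | 22.4/28 = 80% |
| In hospital to D5, light stopped by the rule, 1 day used | 29.8/40 = 74.5% | 27.6/40 = 69.0% | 25.4/40 = 63.5% |
| Same, no day used | 28.8/40 = 72% | 25.6/40 = 64% | 22.4/40 = 56% |
| Left hospital on D2, 1 intended day, used | 29.8/37 = 80.5% | 27.6/34 = 81.2% | 25.4/31 = 81.9% |
| Left hospital on D2, 1 intended day, not used | 28.8/37 = 77.8% | 25.6/34 = 75.3% | 22.4/31 = 72.3% |

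The crossing of 70% also depends on the 80%. With one used day per removed patient and four intended days charged, 90% use still gives (25.2 + 3)/40 = 70.5% at d = 3. With 75% use the result is (27 + 1)/40 = 70.0% at d = 1 and (24 + 2)/40 = 65% at d = 2.

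**5. The other metrics**
Acceptance is settled when light is offered, before any removal. Tolerance is conditional on exposure, and an ICU transfer is not intolerance. Fidelity is a share of time per day. Removal could move tolerance or fidelity either way.

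**The case against.** A reader might infer that the rule inflates feasibility in general and breaks the randomised comparison. The documents do not support that.

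- They never say that removed patients' days leave the denominator. Only sustainability has a clear upward direction, and only if those days are dropped.
- The fall below 70% needs patients who stay in hospital through D5 and lose light because of the rule. Those who leave hospital on D2 barely change the result.
- The rule is the same in all three arms, and nothing shows that ICU departure by D2 differs by arm.
- The rule has an evident purpose. Aim 1 Research Design stops urinary aMT6s at MICU discharge, so a patient who leaves on D2 has no complete post-light night of outcome data. Keeping that patient cannot supply it.
- The entry criterion is a minimum forecast, not a cap, and it nearly matches the timeline cut-off.
- The Aim 3 rule could be read as overriding the general timeline.

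All of this limits the size of the point. It does not remove it. No precedence between the two rules is stated. An incomplete outcome can justify an outcome-evaluable subset, but it does not require removal from the study, and the feasibility metrics need no aMT6s.

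**Conclusion.** The conflict between the two cut-offs is plain in the text. That removal follows assignment is an inference from the 09:00 start on D2, and a safe one for anyone treated that day. The entry criterion admits patients who may be expected to fail the later cut-off. With no analysis set or denominator stated, sustainability may be overstated and the between-arm effect size may be biased in an unknown direction. Acceptance is unaffected.

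In the illustration two removals among 10 light patients change the verdict (80% to 69%). This rests on 80% use, four intended days, one used day per removed patient, continued hospital stay through D5, and light stopped by the rule. The exponential stay model makes about one to three such removals plausible under the later cut-off, but it does not establish how many would remain in hospital. The point should be settled before the data are analysed. It is not a demonstrated failure of the pilot.

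**What to change.** 1. Reconcile Timeline of Study Activities and Aim 3 Research Design to one cut-off. The choice is the sponsor's; the steps below work with either.
2. Count every patient randomised to light in the feasibility metrics, with intended days defined as D2-D5 while in hospital. State the denominator of each metric.
3. Make the all-randomised set primary for the arm comparison, using whatever aMT6s was collected up to MICU discharge.
4. Label patients who meet the cut-off as an outcome-evaluable subset, and acknowledge that early leavers contribute little post-light aMT6s.
5. Report removals by arm with reasons, and state whether removed patients are replaced.

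The cost is mainly wording and slightly more reporting. Each removed patient's hospital discharge date must be kept so that the intended days can be counted. Feasibility percentages may come out slightly lower. The missing circadian outcome in early leavers remains.
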